3.2.4 Immunogenicity Endpoints and Associated Variables

Blood samples for determination of ADA in serum will be collected as specified at timepoints mentioned in the SoA ([Table 2](#) and [Table 3](#)).

Immunogenicity parameters are:

- ADA
- Immunogenicity titre

These parameters are tested in an external laboratory. A validated screening assay will be used to determine ADA positive samples. Any positive samples will be tested in a confirmatory assay whereby the specificity of the ADA response will be confirmed as either positive or negative with respect to AZD1402. Titre evaluations are performed on samples that are confirmed positive for ADA.

Anti-drug antibodies will be defined as positive when titre measurements reported as ≥ 10 (minimum required dilution).

All these parameters are assigned to the analysis visits and to the analysis phases as described in [Figure 1](#) and [Figure 2](#) of Section 3.1.2. Measurements with missing or partial missing dates are not assigned to any analysis visit.

The study day of ADA measurement is calculated as the date of the ADA sample collection – the date of first IP +1 for ADA sample collected on or after the day of first IP and as the date of the ADA sample collection – the date of first IP for ADA sample collected before the day of first IP.

3.2.5 Exploratory Endpoints and Associated Variables

Part 1:

The exploratory endpoints for Part 1 are:

- Change from baseline in FeNO at Day 28 and average over the Treatment Period.
- ~~CCI~~
- Change from baseline average in cough VAS over the Treatment Period.

Statistical Analysis Plan

For details on these assessments except cough VAS, refer to Section 3.1.2.

Part 2:

The exploratory endpoints for Part 2 are:

- Change from baseline in FeNO (in-clinic).

3.2.5.1 Cough VAS

In Part 1 participants will be asked to complete a cough severity VAS (100 mm linear scale marked with a horizontal line by the participant, with 0 mm representing “no cough” and 100 mm representing “worst cough”) measuring subjective assessment by the participant for the prior 24 hours for severity of cough symptoms. More details on the Cough VAS are included in the Appendix H of CSP.

3.2.5.2 CCI

CCI

3.2.5.3 CCI

CCI

3.2.5.4 CCI

CCI

3.2.5.5 Fractional Exhaled Nitric Oxide

For details on this assessment, refer to Section 3.2.1.4.

3.2.5.6 Cough VAS

For details on this assessment, refer to Section 3.2.1.2.

4 STATISTICAL METHODS**4.1 Data Quality Assurance**

All tables, figures, and data listings to be included in the report will be independently checked for consistency, integrity and in accordance with standard Parexel procedures.

4.2 General Presentation Considerations

‘Baseline’ (unless stated otherwise) is defined as the last available pre-treatment assessment. ‘End of Study’ is defined as the last available post-treatment assessment. ‘Treatment Day’ will be calculated

Statistical Analysis Plan

relative to the date of randomisation, ie, Treatment Day = Assessment Date - Randomisation Date + 1.

All variables, if not otherwise specified, will be summarised by each Part (Part 1 and Part 2) and study treatment group (dose level of AZD1402 or placebo) and AZD1402 overall (when required), using descriptive statistics, tables and/or figures, as applicable.

Continuous data will in general be summarised in terms of the mean, standard deviation (SD), median, minimum, maximum, and number of observations. Continuous data that are expected to be skewed will be presented in terms of the maximum, upper quartile (Q3), median, lower quartile (Q1), minimum and number of observations.

The same level of precision should be used for means, SD, SE, and CIs. The minimum and maximum values would normally be reported to the same number of decimal places as the individual values, unless a decision has been made to report the summary statistics to a lesser number of decimal places than the original data. Medians may be presented to 1 more decimal place than the recorded values to account for ties.

In general, the maximum number of decimal places reported shall be 4 for any summary statistic. These summaries will be provided by timepoint of assessment as appropriate. If at a given timepoint, $n < 3$, then only n , minimum and maximum will be presented. If $n = 3$, then only n , mean, median, minimum, and maximum will be presented. The other descriptive statistics will be left blank.

A missing category shall be included only for categorical variables where no data is available. The missing category will be omitted if there were no missing values for that variable. Categorical data will be summarised in terms of the number of subjects providing data at the relevant time point (n), frequency counts and percentages.

Percentages will be presented to 1 decimal place. Percentages will not be presented for zero counts. Percentages will be calculated using n as the denominator. If sample sizes are small, the data displays will show the percentages, but any textual report will describe frequencies only.

Changes from baseline in categorical data will be summarised using shift tables where appropriate.

All confidence intervals (CIs) will be 2-sided 95% CIs, unless stated otherwise, and presented to one more decimal place than the raw data recorded in the database. If a model is used to estimate the treatment difference, the corresponding CI according to the model will be presented. Otherwise, the unadjusted CI will be used. Nominal p-values may also be presented. Care should be taken when interpreting CIs and p-values since no correction for multiple testing is done for the endpoints.

P-values greater than or equal to 0.001, in general, will be presented to 3 decimal places. P-values less than 0.001 will be presented as “<0.001”.

Descriptive statistics for calculated PK parameters and FeNO will include: n , mean, SD, geometric mean, geometric coefficient of variation (GeoCV%), median, minimum and maximum values.

The GeoCV% will be calculated as $SQRT(es^2-1)*100$ where s is the SD of the log-transformed values.

Daylight saving dates will be considered in the calculation of the absolute scheduled and actual times and in the duration when this is based on times. Therefore, if any daylight saving change occurs during the study development, this will impact the description of the blood sample collections, the calculation of the PK parameters and any AE duration in case the time is included in the calculation of the duration.

Statistical Analysis Plan

All other requirements and specifications for programming and presentation of TFLs will be specified in the TFL shells document.

The following rules will be applied for any repeated safety assessments:

- For repeated assessments at any timepoint before first IP administration (including screening values and baseline): the latest assessment obtained per timepoint will be used in the calculation of descriptive statistics.
- For repeated assessments at any timepoint after first IP (including Follow-up visit): the first (non-missing) value after dosing will be used in the calculation descriptive statistics.

The AM and PM assessments will be combined into a daily assessment according to the following formula:

Let assessment (Day i) = (PM assessment (Day i) + AM assessment Day (i+1)) / 2

4.3 Software

All report outputs will be produced using SAS® version 9.4 in a secure and validated environment.

PK parameters will be calculated using Phoenix® WinNonlin (WNL) version 8.1 or a later version in a secure and validated environment.

All TFLs will be presented in individual files (.rtf or.docx) and also in one portable document format (PDF and.docx) book-marked document containing all Tables and Figures (14.x outputs) combined and distinct PDF book-marked files for each of the 16.2.x subsections, ie, one for all 16.2.1.x outputs, one for all 16.2.2.x outputs, etc.

4.4 Study Subjects

4.4.1 Disposition of Subjects

A clear accounting of the disposition of all subjects who enter the study will be provided for each study part, from screening to study completion.

Subject disposition will be summarised for screening failures (in the screening phase), subject discontinuation during Run-in phase, randomised subjects separately for each study part. Screening failures data will be summarised based on the subjects enrolled in the study.

The following information will be provided:

- Number of subjects screened.
- Number of screening failures including the reason of failing.

Disposition summaries of randomised subjects will be presented for each study Part by treatment group (each dose level of AZD1402, placebo, and pooled AZD1402), and overall and include the following information:

- Number of subjects randomised.
- Number of subjects randomised, not treated, including the reason.
- Number and percentage of subjects who started treatment.
- Number and percentage of subjects who completed treatment.

Statistical Analysis Plan

- Number and percentage of subjects who discontinued treatment, including the reason.
- Number and percentage of subjects who completed study part.
- Number and percentage of subjects who withdrawn from study part, including the reason.
- Number and percentage of subjects who discontinued treatment due to global/country situation
- Number and percentage of subjects who withdraw due to global/country situation.

Percentage will be based on number of subjects started the treatment.

A disposition figure will be also presented for each treatment and study part.

The global country situation study disruption will be summarised.

A subject who completed the study Part is defined as a subject who completed all scheduled visits including the Follow-up visit.

A subject who completed the treatment is defined as a subject who completed the treatment period.

Subjects' discontinuations will be listed including the date of study discontinuation, treatment duration exposure (in days) as well as reason for discontinuation for each study part.

Subject affected by the global/country situation will also be presented in listings.

The number of subjects recruited per country/site will be also summarised by analysis population and treatment group.

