4.4 End of Study Definition

For the purpose of CTT the definition of the end of the study differs under FDA and EU regulatory requirements:

European Union requirements define study completion as the last visit of the last subject for any protocol related activity.

Food and Drug Administration requirements defines two completion dates:

Primary Completion Date – the date that the final participant is examined or receives an intervention for the purposes of final collection of data for the primary outcome measure, whether the clinical study concluded according to the pre-specified protocol or was terminated. In the case of clinical studies with more than one primary outcome measure with different completion dates, this term refers to the date on which data collection is completed for all of the primary outcomes.

Study Completion Date – the date the final participant is examined or receives an intervention for purposes of final collection of data for the primary and secondary outcome measures and AEs (for example, last participant's last visit), whether the clinical study concludes according to the pre-specified protocol or is terminated.

A participant is considered to have completed the study if he/she has completed all periods of the study including the last scheduled procedure shown in the SoAs ([Table 1](#) and [Table 2](#)).

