- Any other AE that, in the opinion of the Investigator or the Sponsor, warrants discontinuation of further dosing of study intervention.
- Haematologic toxicity defined as 1 or more of:
 - Confirmed leucocyte count $< 2.0 \times 10^9/\text{L}$.
 - Confirmed neutrophil count $< 1.0 \times 10^9/\text{L}$.
 - Confirmed platelet count $< 75 \times 10^9/\text{L}$.
 - Confirmed lymphocyte count $< 0.5 \times 10^9/\text{L}$.
- Symptomatic bradycardia defined as heart rate $< 45 \text{ bpm}$ or asymptomatic bradycardia defined as resting supine pulse $< 30 \text{ bpm}$ while awake persisting for at least 10 minutes.
- Hepatic toxicity defined as 1 or more of:
 - Confirmed ALT or AST increase to $> 3 \times \text{ the ULN}$.
 - Confirmed isolated TBL increase to $> 2 \times \text{ ULN}$.
 - Confirmed ALT or AST increase to $> 2 \times \text{ ULN}$ concurrent with an increase in TBL to $> 1.5 \times \text{ ULN}$.
- A severe asthma exacerbation as defined in Section 8.1.5.
- Confirmed diagnosis of COVID-19 (Part 1 only).
- COVID-19 vaccination** during the study (Part 1 only).

*Baseline Part 1: Mean of Day -1 and Day 1; Baseline Part 2: Mean of Day 1 (15 minutes and 45 minutes pre-dose).

** In Part 1, if the participant is vaccinated during the study, study intervention will be discontinued. The participant will be followed up and included as part of the safety population.

Participants in Part 1 of the study who are permanently discontinued from receiving the study intervention will be followed for protocol specified assessments and follow-up of any AEs as indicated clinically unless consent is withdrawn from further study participation or the participant is lost to Follow-up. Unscheduled assessments for safety may be performed if required. Where possible, participants in Part 1 should follow the PK sampling time frame associated with the last dose as per SoA ([Table 1](#)) for Days 28-32 or as directed by the Study Physician. An IPD Visit followed by both follow-up at visits (11 and 28 days after the last study drug intake) may be performed at the Investigator's discretion if visits as per protocol SoA ([Table 1](#)) are not required for safety follow-up.

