 - Logistical improvements of the site and structural measures of the study site building will be implemented to further improve physical distancing.
 - If, for reasons related to the COVID-19 pandemic (eg, local lockdown, self-isolation requirements), a participant is not able to attend their scheduled visit within the visit window, they can have their visit rescheduled as detailed in the study reference manual/as per agreement with the Sponsor study physician. Where visits cannot be rescheduled, participants should continue at the next scheduled visit. Additionally, on-site visits may be replaced by a telemedicine visit if allowed by local/regional guidelines. Having a telemedicine contact with the participants will allow collection

of data for AEs, concomitant medications, adherence to the e-Diary and PRO measures to be reported and documented. The term telemedicine visit refers to remote contact with the participants using telecommunications technology including phone calls, virtual or video visits, and mobile health devices.

- If site visits are not possible due to local restrictions, home nursing visits may be considered after discussion with and approval by the Sponsor according to local regulations. The Principal Investigator will be responsible to delegate any study procedure, however the Principal Investigator will retain responsibility for evaluation of the data collected. In all cases, informed consent should always be collected in writing.

F 3 Restrictions Related to COVID-19

During the COVID-19 pandemic, participants are advised to adhere to local requirements for reduction of the public SARS-CoV-2 exposure while ambulatory. If applicable, prior to Screening (Visit 1), potential participants should be called to confirm they are not experiencing any COVID-19 symptoms and signs and are asked not to attend the site in case of suspected infection. If appropriate, participants will be referred to the local health care system. Physical distancing and person-to-person contact restrictions will be applied and explained to participants while staying at the study site. Where physical distancing is not possible, study participants will be asked to use surgical face masks and/or gloves if deemed appropriate by the Investigator and site staff and guided by local requirements.

F 4 Data Quality Assurance Related to COVID-19

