Part 1 will contain a total of 11 visits, and at Visit 7 participants will complete the Treatment Period. Two outpatient visits for safety and PK (Visit 8 and 9) are scheduled 1 and 3 days after discharge from the clinic. A follow-up (Visit 10) will occur 1 to 2 weeks following Visit 7, and a second and final follow-up (Visit 11), will occur 4 weeks after Visit 7.

3.1.2 Part 2

Part 2 will be randomised, double-blind, placebo-controlled and will include approximately 165 participants to evaluate 2 inhaled dose levels (^{CCI} mg and ^{CCI} mg) of AZD1402 against placebo. Approximately 5 participants will be randomized to ^{CCI} mg and 80 participants will be randomized to ^{CCI} mg and placebo, respectively. The number of subjects enrolled in the ^{CCI} mg dose will depend on the enrolment rate and the randomisation ratio will change during the study. Patients will be randomised 2:1 (active to placebo) whilst the ^{CCI} mg arm is ongoing. Once the ^{CCI} mg has stopped recruiting and randomisation continues in the ^{CCI} mg and placebo arms, the randomisation ratio will be 1:1 (active to placebo).

Part 2, will be started after the unblinded safety review for Part 1a

Part 2 will include:

[figure not shown]
- AZD1402 inhalation ^{CCI} mg ^{CCI} [REDACTED]
- AZD1402 inhalation ^{CCI} mg ^{CCI} [REDACTED]
- Placebo inhalation ^{CCI} [REDACTED]

Part 2 will contain a total of 9 visits, and at Visit 7 participants will complete the Treatment Period. A follow-up (Visit 8) will occur approximately 1 to 2 weeks following Visit 7, and a second and final follow-up (Visit 9), will occur approximately 4 weeks after the end of treatment.

The entire study period for each participant in both Parts 1 and 2, is approximately 3.5 months; a 2-week Screening Period, a 4-week Run-in Period, 4 weeks of Treatment Period, and 4 weeks of Follow-up Period.

Figure 1

Study Design Part 1

[figure not shown]

CCI [REDACTED]; SRC = Safety Review Committee; wks = weeks.

Participants may also be required to attend a Visit up to 2 years after randomisation for a follow-up ADA sample.

Figure 2

Study Design Part 2

CCI [REDACTED]

SRC = Safety review committee

The Schedule of Assessments (SoA) for the Part 1 and Part 2 are provided in [Table 2](#) and [Table 3](#) of Appendix 5.1. Further details regarding the study design are provided in Section 4 of the CSP.

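### SAP 4.4.1 counts study completers by attendance at every scheduled visit, which conflicts with CSP 4.4 and leaves some participants neither completed nor withdrawn

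*SAP*

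**What the plan says.** SAP 4.4.1 plans a disposition table of randomised participants, by treatment group and study part. It gives two completion rules. For the study part: "A subject who completed the study Part is defined as a subject who completed all scheduled visits including the Follow-up visit". For treatment: "A subject who completed the treatment is defined as a subject who completed the treatment period". The second carries no condition on dosing.

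Separate rows report the "Number and percentage of subjects who discontinued treatment, including the reason" and the "Number and percentage of subjects who withdrawn from study part, including the reason". The same section bases all percentages on participants who started treatment, although the table also has rows for those randomised, those randomised but not treated, and those who started treatment.

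CSP 4.4 defines study completion differently: "A participant is considered to have completed the study if he/she has completed all periods of the study including the last scheduled procedure". It does not ask for every visit.

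**The concern.** A disposition table should place each participant in exactly one study-status row and exactly one treatment-status row. The SAP rules do not ensure this.

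- **Study status.** The SAP is stricter than the protocol, and no row is provided for people who fail the SAP rule without withdrawing.
- **Treatment status.** In Part 1 the wording allows one person to be counted as having both completed and discontinued.
- **Denominator.** One of the planned percentages carries no information.

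At stake is whether reported retention agrees with the protocol's own definition and whether the table reconciles. No efficacy inference depends on it.

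**Working it through.** The documents state no completion rate, so there is no figure to reproduce. The check compares the rules, follows individual cases through them, and then illustrates the size.

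**1. Missed interim visit.** For visits lost to COVID-19 reasons, CSP Appendix F 2 says: "Where visits cannot be rescheduled, participants should continue at the next scheduled visit". Take a Part 2 participant who misses Visit 5 and attends Visits 6 to 9.
- CSP 4.4: all periods and the last procedure are done, so completed.
- SAP 4.4.1: not all visits were attended, so not completed. The participant never withdrew, so not withdrawn.

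**2. Early stop of drug in Part 2.** Under CSP 7.1.1 such a participant has an intervention discontinuation (IPD) visit and then follow-up visits 11 and 28 days after the last intake. Suppose drug stops between Visits 4 and 5, so that Visits 5 to 7 are not attended.
- SAP 4.4.1: not completed, however complete the follow-up.
- CSP 7.1.1 treats discontinuing the intervention as distinct from withdrawing from the study, so not withdrawn either.
- CSP 4.4 does not settle the case, because it does not say whether a shortened treatment period counts as completed.

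This gap needs no assumption about missed visits. It also arises in Part 1 when the investigator uses the IPD route.

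**3. Size of the missed-visit effect (illustration).** A finisher has by definition attended the last visit, so only interim visits can be missed: Visits 4 to 8 in Part 2 (k = 5) and Visits 4 to 10 in Part 1 (k = 7). With an assumed miss probability m per visit, independent across visits, the share of finishers not counted is 1 − (1 − m)^k. The planned numbers are 80 per main arm in Part 2 and 45 in total in Part 1.

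| m (assumed) | Part 2 share | of 80 | Part 1 share | of 45 |
|---|---|---|---|---|
| 0.5% | 2.5% | 2.0 | 3.4% | 1.6 |
| 1% | 4.9% | 3.9 | 6.8% | 3.1 |
| 2% | 9.6% | 7.7 | 13.2% | 5.9 |
| 3% | 14.1% | 11.3 | 19.2% | 8.6 |
| 5% | 22.6% | 18.1 | 30.2% | 13.6 |

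For example, 1 − 0.95^5 = 0.226, and 0.226 × 80 = 18.1.

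**4. Treatment completer, Part 1.** SAP 3.1.1 places the end of treatment at a visit: "Part 1 will contain a total of 11 visits, and at Visit 7 participants will complete the Treatment Period". CSP 7.1.1 keeps people on the schedule after stopping drug: "Participants in Part 1 of the study who are permanently discontinued from receiving the study intervention will be followed for protocol specified assessments". A participant permanently off drug who still attends Visit 7 can therefore be read as a treatment completer while also standing in the discontinued row. Active arms have about 10 participants (Part 1a: 30 / 3; Part 1b: 15 × 2/3), so one such person moves the completed row by 1/10, or 10 percentage points. Completed plus discontinued would then total 11 of 10.

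**5. Denominator.** The percentage who started treatment is the number started divided by the number started, always 100%. The SAP also does not say whether a participant who was randomised, not treated and then withdrew enters the withdrawn row. If so, the numerator holds someone who is outside the denominator.

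**The case against.** The case for leaving the text alone has substance.

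- **Missed visits may be few.** The rule about continuing at the next visit sits in the COVID-19 appendix and applies only when rescheduling fails. CSP 7.3 tells sites to reschedule missed visits, and home or telemedicine visits may replace site visits. SAP 4.4.2 already lists out-of-window visits and procedures not performed as important deviations. This stands as a reason to expect the lower end of the range, but it does not give the affected participants a row, and it does not touch the early-stop case.
- **The Part 1 overlap is narrow.** The SAP speaks of completing the treatment period, not merely reaching its end. The Part 1 FEV₁ discontinuation rule sends participants into follow-up, and the IPD route is available. In Part 2 the overlap does not arise, because those who stop drug leave the treatment visits. This stands: it is an ambiguity, confined to Part 1 participants kept on assessments while off drug.
- **Treated participants are a natural denominator.** They match the FAS and Safety Set, and the untreated are reported with reasons, so a reader can convert. This is fair for on-treatment rows. It does not rescue a percentage fixed at 100%.

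A reader might infer that the drug will look better tolerated than it is, so that tolerability and completion err in opposite directions. The documents do not support that. Treatment completion is not among the Part 1 primary safety endpoints in CSP Table 3. Early stopping is reported through the discontinued row with reasons, adverse events leading to discontinuation (SAP 4.17.1), exposure net of interruptions (SAP 4.9.1) and compliance against 55 planned doses (SAP 4.9.2).

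**Conclusion.** The point holds as a defect of reporting. The SAP's study-completer rule conflicts with CSP 4.4 and leaves identifiable participants in neither the completed nor the withdrawn row.

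For missed interim visits the direction is clear: completion is understated relative to the protocol. The size, about 2 to 18 of 80 per arm in Part 2, rests wholly on an assumed miss rate of 0.5% to 5%, on independence between visits and on planned arm sizes. SAP 4.20 refers to anticipated closure, so actual numbers may be smaller. For Part 2 participants who stop early the gap follows from the text alone, but its size depends on how many stop, which the documents do not state.

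The Part 1 treatment-completer wording is ambiguous rather than wrong, and the denominator rule makes one row uninformative.

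Nothing here changes the primary analysis, the analysis sets or power. The FAS and Safety Set depend on randomisation and receipt of study intervention, not on completion.

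**What to change.** Amend SAP 4.4.1 in three places.

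(a) Take the study-completer definition from CSP 4.4 and do not require every interim visit; report missed visits separately. State in which row participants who stop drug but complete the required follow-up are counted, so that completed and withdrawn are mutually exclusive and together exhaustive.

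(b) Define a treatment completer as a participant who reached the end of the treatment period without permanent discontinuation of study drug. Completed and discontinued then cannot overlap. A single missed last dose is a matter for compliance, not for this row.

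(c) Use the number randomised as denominator for the started, not-treated and withdrawn rows. The study-completed row should share the withdrawn row's denominator so that the two can be added.

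The cost is a few sentences and a change to the disposition derivation. It should need no new data collection: CSP 6.4.2 has medication start and stop dates recorded in the eCRF, and SAP 4.4.1 already tabulates discontinuations and withdrawals with reasons.
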